This study is an investigation of 97 subjects who have expressed interest in using CBD for anxiety. Subjects will complete study visits at McLean Hospital. Following a preliminary phone screen and prior to any evaluation, all study subjects will be required to sign a McLean Hospital approved informed consent form that describes all study procedures. The phone screen includes questions related to medical history, substance use history, demographics, and screening questions from the OASIS (see below) to determine whether the subject has anxiety.

Individuals will be assessed at baseline and weekly for four weeks of treatment with compounds administered as sublingual tinctures in a double-blind, randomized procedure: subjects will receive either a full-spectrum high CBD product, a single-compound CBD product, or matched placebo in a 3:1:1 randomization schedule. Each product will be analyzed and verified at an outside lab for safety and potency. Subjects will self-administer 1 ml (10mg/ml) of CBD or placebo sublingually three times daily. At each weekly visit, individuals will complete clinical scales and have a check-in with study staff. Neuropsychological testing will be performed at baseline and the final visit in order to assess cognitive performance. Buccal swabs will be collected for DNA analysis from all participants in the double-blind phase, and a subset of

individuals will complete blood draws at baseline and week 4 in order to assess levels of circulating endocannabinoids. Finally, a subset of individuals will receive an hour-long MRI scan at baseline and the final visit, with both resting state and task-related functional magnetic resonance imaging (fMRI) in each MRI session. In addition, a brief diffusion tensor imaging (DTI) sequence will also be acquired to examine white matter fiber tract integrity, and magnetic resonance spectroscopy (MRS) will be conducted to examine levels of certain metabolites in the brain.

At the investigators' discretion, in order to assess clinical state, participants may complete daily mood ratings either on paper or electronically via REDCap or StudyTrax. Additionally, subjects will be given the option to complete study drug diaries manually (pencil and paper) or via a secure web portal.

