In order to assess the efficacy of the dose chosen for the double-blind study, we will also conduct a small open-label phase I trial of the full-spectrum CBD tincture prior to initiating the double-blind study. This open-label trial will enroll up to 22 participants who are interested in using CBD, and who have anxiety. This trial will determine whether patients derive clinical benefits at the current dosage proposed for the active treatment arm of the double-blind trial. This trial will examine all components of the originally proposed study. During the open-label phase, a subset of participants (up to n=16) will complete an extra visit that includes clinical rating scales and a 2-hour continuous blood draw directly following administration of the tincture in order to assess plasma concentration of CBD over time and correlation with anxiety.

Subjects will be recruited through IRB-approved advertisements and flyers in regions that have approved medical marijuana. Additionally, medical marijuana healthcare facilities throughout New England, including CannaCare, Integr8, MMJ Physician Practice, and others, may also refer interested patients to contact the study recruitment line for further screening. These healthcare groups provide their interested patients who meet for general inclusion criteria with study recruitment materials. The total sample size for the double-blind study is 75 (45 full-spectrum CBD, 15 single-compound CBD, and 15 placebo); up to 15 of each group (45 total) will also complete the MRI scanning protocol. For the open-label trial, the total sample size is 16 (we will enroll up to 22 to ensure 16 completers); up to 16 subjects will complete the MRI scanning protocol.

Inclusion Criteria

- 1) Subject has provided informed consent
- 2) Subject is 18 or older
- 3) Subject is a native English speaker or acquired English prior to age 5
- 4) Subject scores a minimum of 16 on the Beck Anxiety Inventory (BAI) OR a minimum of 11 on the Overall Anxiety Severity and Impairment Scale (OASIS) at the screening/baseline visit or at phone screening if within 2 weeks of the baseline visit

Exclusion Criteria

Subjects will be excluded if they report any of the following:

- 1) Non-native English speakers
- 2) Estimated IQ < 75
- 3) Meets criteria for DSM-V classification of current substance abuse/dependence, a psychotic disorder, bipolar disorder, or an eating disorder

- 4) A history of head injury or loss of consciousness greater than 5 minutes

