Subjects will meet with the Principal Investigator, a Clinical Neuropsychologist, or a trained Research Assistant at McLean Hospital for five visits (baseline, and four weekly visits throughout the four-week treatment period). A subset of subjects in the open-label phase will also complete an optional 6th visit; this visit will occur after a >1 week washout period after the final (week 4) visit, where they will return to the lab to complete a 2-hour continuous blood draw after administration of the tincture. Subjects will review and sign the approved informed consent form prior to engaging in any study procedures. A structured clinical screening interview (SCID-P or QuickSCID) will be administered, and demographic information, substance abuse/use, and medical histories will also be obtained. Study inclusion/exclusion criteria will be applied, and appropriate subjects will be enrolled and complete the rest of the study visit, which will consist of clinical ratings and quality of life scales, a neuropsychological assessment, a driving simulation task, and an hour-long MRI scan for a subset of eligible individuals. The imaging protocol will include structural and functional imaging techniques, as well as diffusion tensor imaging/diffusion kurtosis imaging and magnetic resonance spectroscopy.

The baseline visit is estimated to take approximately 6-7 hours, and the final study visit is estimated to take approximately 3-4 hours, with the weekly visits in the interim estimated to take approximately 1 hour, for a total of approximately 12-14 hours required to complete all possible visits. The optional 6th visit will take approximately 3 hours to complete. [REDACTED]

[REDACTED] urine samples will be collected at each visit to measure THC and other substance levels throughout the study. Female subjects who enroll in the study will be informed that their sample will also be used to confirm negative pregnancy (HCG) status (QuPID One-Step Pregnancy). A buccal swab sample will also be collected for DNA analysis in the double-blind phase.

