Standard of care for anxiety treatment includes medications, such as antidepressants, buspirone, and benzodiazepines, as well as psychotherapy. This study is an investigation of a plant-derived compound that has promise in the treatment of anxiety. Subjects will not be asked to change their current treatment regimen to participate in this study (i.e. discontinue other medications); this study will add CBD to their current regimen.

Describe how risks to subjects are minimized, for example, by using procedures which are consistent with sound research design and which do not unnecessarily expose subjects to risk or by using procedures already being performed on the subject for diagnostic or treatment purposes.

Risks to subjects will be minimal throughout this study; please see below for detailed explanation of foreseeable risks and discomforts. The components of this study, including the clinical rating scales, neurocognitive tasks, and MR scanning have previously been used by the investigator in multiple studies. The administration of CBD will be low risk due to the add-on design of the study; patients will proceed with their treatment as usual, with CBD or placebo added to their medication regimen. See below for a detailed explanation of the risks of CBD administration in this population.

Describe explicitly the methods for ensuring the safety of subjects. Provide objective criteria for removing a subject from the study, for example, objective criteria for worsening disease/lack of improvement and/or unacceptable adverse events. The inclusion of objective drop criteria is especially important in studies designed with placebo control groups.

The side-effect profile of CBD is extremely low, and adverse events are not anticipated. Subjects may withdraw from the study at any time and for any reason. A subject's participation in the trial will end if they report adverse effects of CBD or placebo administration and wish to leave the study, or if study staff determine that study termination is appropriate due to adverse events.

FORESEEABLE RISKS AND DISCOMFORTS

Provide a brief description of any foreseeable risks and discomforts to subjects. Include those related to drugs/devices/procedures being studied and/or administered/performed solely for research purposes. In addition, include psychosocial risks, and risks related to privacy and confidentiality. When applicable, describe risks to a developing fetus or nursing infant.

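### Nothing in the plan requires or tracks stable anxiety treatment, so the open-label phase and the per-arm pre-post tests can credit a recently started treatment's effect to CBD

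*Combined protocol and SAP*

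**What the plan says.** The standard-of-care part of Research Design and Methods lists the background treatments in view: "Standard of care for anxiety treatment includes medications, such as antidepressants, buspirone, and benzodiazepines, as well as psychotherapy". It keeps them in place: "Subjects will not be asked to change their current treatment regimen to participate in this study (i.e. discontinue other medications". The paragraph on minimising risk repeats this: "patients will proceed with their treatment as usual, with CBD or placebo added to their medication regimen".

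Entry on anxiety is by score alone: "Subject scores a minimum of 16 on the Beck Anxiety Inventory (BAI) OR a minimum of 11 on the Overall Anxiety Severity and Impairment Scale". None of the 4 inclusion and 8 general exclusion criteria concerns recent starts, stops or changes of anxiety medication or psychotherapy. Medical history is taken at baseline and staff check in weekly, but neither is tied to treatment changes.

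Follow-up is short: "five visits (baseline, and four weekly visits throughout the four-week treatment period". In the double-blind phase, "subjects will receive either a full-spectrum high CBD product, a single-compound CBD product, or matched placebo in a 3:1:1 randomization schedule". Its size is given as follows: "The total sample size for the double-blind study is 75 (45 full-spectrum CBD, 15 single-compound CBD, and 15 placebo".

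The open-label phase has 16 planned completers, all on the full-spectrum product. Of this phase the protocol says: "This trial will determine whether patients derive clinical benefits at the current dosage proposed for the active treatment arm of the double-blind trial". Under Data and Safety Monitoring, clinical response is assessed after the first 5 completers, and the double-blind phase waits for an adequate dose/response.

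Statistical Approaches specifies mixed-model ANOVAs with between-group post hoc tests, plus a post hoc comparison of baseline with post-treatment data inside each arm. No covariate or stratum for background treatment is named. Specific Aim 1 is itself worded as a pre-post comparison.

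**The concern.** A person who began an antidepressant or a course of psychotherapy shortly before baseline is eligible. If that treatment produces any improvement within the four weeks, the improvement falls inside the observation window.

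A before-and-after comparison cannot separate it from an effect of CBD. The plan relies on such comparisons in two places: the open-label phase, which informs whether the double-blind phase starts, and the per-arm tests. Placebo control does not protect a per-arm test, because that test never looks at the placebo arm.

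The 3:1:1 allocation adds a trap. The same background improvement is more likely to reach significance in an arm of 45 than in one of 15, which invites the reading that CBD worked and placebo did not. Without a record of changes, nobody could examine this afterwards.

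**Working it through.** **The plan's own figure.** The only stated calculation is a minimum of 45 participants (f=0.20, power 85%, alpha 0.05). It is reproduced for a group-by-time interaction with 3 arms, 5 visits, an assumed correlation of 0.5 and sphericity: power at 45 is 86.1%. It is not in dispute and does not bear on this point.

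**Inputs.** From the documents: arms of 45, 15 and 15; 16 open-label completers; a look at 5. Assumed, because the documents give neither: a share q of subjects with recently changed treatment (10-40%), and their extra four-week improvement g (0.3-0.8 SD of change). The true CBD effect is set to zero.

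**1. Within-arm tests.** Statistical Approaches calls these independent t-tests; a paired test of change is used here because the same subjects are measured twice.
- Spurious mean improvement = q × g. Range: 0.1 × 0.3 = 0.03 SD to 0.4 × 0.8 = 0.32 SD.
- SD of change = √(1 + q(1−q)g²). At q=0.2, g=0.5: √1.04 = 1.02. At q=0.4, g=0.8: √1.154 = 1.074.
- Noncentrality = (q × g / SD) × √n. At q=0.2, g=0.5, n=45: (0.10/1.02) × 6.708 = 0.66. At q=0.4, g=0.8, n=45: (0.32/1.074) × 6.708 = 2.00.
- Chance that the two-sided 5% test rejects, from the noncentral t distribution:

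| q, g | n=15 | n=16 (open-label) | n=45 |
|---|---|---|---|
| 10%, 0.3 SD | 5.1% | 5.1% | 5.4% |
| 20%, 0.5 SD | 6.5% | 6.6% | 9.9% |
| 40%, 0.8 SD | 19.0% | 20.1% | 49.8% |

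**2. Look at 5 completers.** The chance that at least one recently changed treatment is 1 − (1−q)⁵: 41% at q=10%, 67% at 20%, 83% at 30%, 92% at 40%. This shows exposure, not that the decision would change.

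**3. Randomised comparison, 45 v 15, changes made before baseline.**
- Simulated mean difference is about 0 and type I error is 5.2-5.3% at (20%, 0.5 SD) and (40%, 0.8 SD). There is no systematic bias.
- SD of the difference in shares = √(q(1−q)(1/45 + 1/15)): 9 percentage points at q=10%, 12 at 20%, 15 at 40%. A gap of 20 points or more occurs in 3%, 11% and 20% of trials respectively.
- At q=0.2, g=0.5 the resulting shift has SD 0.119 × 0.5 = 0.06 SD of change. The standard error of the contrast is 1.02 × √(1/45 + 1/15) = 1.02 × 0.298 = 0.30, so the shift is about one fifth of a standard error.
- Added variance is q(1−q)g²: 4% at that setting, from 0.8% at (10%, 0.3 SD) to 15% at (40%, 0.8 SD).

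**4. Changes after randomisation.** Randomisation does not balance these. If they follow symptoms and occur more often on placebo, the placebo arm improves for another reason and the difference between arms shrinks.

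**The case against.** The strongest reply is that the main phase is randomised, double-blind and placebo-controlled, and its mixed ANOVA has between-group tests. A reader might infer that background treatment biases that comparison towards CBD. The documents do not support this: pre-baseline changes balance in expectation, the 5% error rate holds, and the chance imbalance is already part of the standard error. Later changes, if more frequent on placebo, would work against CBD. This part of the reply stands in full.

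A reader might also infer that the protocol invites subjects to keep changing treatment. It does not say so. It speaks of adding CBD to the current regimen, which reads most naturally as continuation. What can be said is that nothing limits or records changes.

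The prevalence and gain are assumptions, and at the low end the inflation is negligible (5.4% at n=45). That four weeks is long enough for a new treatment to act is likewise assumed.

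Finally, the open-label phase lacks a control for any cause of improvement. Placebo response and regression to the mean would also be credited to CBD, and a stability criterion does not cure that. This stands as well: unstable treatment is one contributor there, though one that is cheap to reduce.

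The add-on design is a deliberate and legitimate choice. A stability window narrows it a little but leaves it intact.

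**Conclusion.** The concern holds for the open-label phase, including the look at 5, and for the per-arm baseline-versus-post tests. There, improvement from recently started anxiety treatment would be attributed to CBD. Under the stated assumptions a paired 5% test rejects in about 10% of trials in the 45-person arm and 6.5% in a 15-person arm (20%, 0.5 SD), rising to about 50% and 19% (40%, 0.8 SD). These figures show the possible range; they are not estimates for this trial.

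For the randomised contrast the cost is limited to modest noise and chance imbalance from pre-baseline changes, plus a possible masking of a difference if later changes are commoner on placebo. This is a cheap improvement, not a flaw that invalidates the double-blind comparison.

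**What to change.** 1. Add an entry criterion that anxiety medication and psychotherapy have been unchanged for a window before baseline. The investigators choose its length. Allow rescheduling, so that no one's care is altered in order to join.
2. Record recent treatment changes at baseline and any change at the existing weekly check-in. Report the counts by arm.
3. State that efficacy claims rest on the between-arm contrast, not on the per-arm pre-post tests. Prespecify one sensitivity analysis that adjusts for recent treatment change at baseline. Prespecify a second that addresses changes after randomisation, labelled supportive because it conditions on a post-randomisation event.
4. Report the open-label response with and without patients whose treatment changed. The protocol gives no responder definition at the look after 5, so side-by-side reporting is more workable than a rule on who counts as a responder.

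The cost is one eligibility line, one question at visits already planned and two short analyses. The downside is small: some applicants wait or are not enrolled, and the population is slightly narrower. If enrolment is too advanced for a new criterion, items 2 to 4 remain worthwhile for subjects still in follow-up and for the analysis.

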A subset of patients in the open-label phase (up to n=16) will complete an optional 6th visit at least one week after completing the open-label phase of the clinical trial. At this visit, an intravenous catheter will be inserted in an antecubital vein for withdrawal of blood samples for subsequent measure of blood CBD and THC levels. The catheter will be inserted 5 to 10 minutes before the sublingual administration of the standard dose of full-spectrum CBD tincture (1mL of 10mg/ml CBD). Blood will be drawn at a maximum rate of 1 mL/min, and five (5) minute samples will be drawn from 5 to 90 minutes after tincture administration and every 10 minutes from 90 to 120 minutes. Quantitative analyses of CBD and THC levels will be performed by gas chromatography. A total of less than 120 mL of whole blood will be drawn on the study day. This method of continuous sampling has been in place and used successfully in [name] laboratory since 1986 (including current approved protocol [REDACTED]).

A subset of patients in the double-blind phase (up to n=75) will complete a blood draw at baseline and week 4. Plasma will be analyzed for circulating levels of endocannabinoids, including: AEA, 2-AG, 2-OG, PEA, and OEA. Levels of cortisol will also be analyzed. Approximately 10ml of whole blood will be drawn into a non-heparinized tube, centrifuged to separate the plasma, flash frozen and transported to [REDACTED]. The samples will be analyzed via mass spectrometry and levels of each endocannabinoid will be assessed pre- and post-CBD treatment.

For the double-blind study, at the end of the baseline visit, eligible subjects will be randomized to either full-spectrum CBD, single-compound CBD, or placebo using a standard 3:1:1 randomization procedure. In the open-label trial, all subjects will be provided with the full-spectrum CBD tincture at the conclusion of the baseline visit. Subjects will be instructed on how to administer the compound in the morning, midday, and evening; they will be instructed how to draw one full dropper of compound, deposit the amount in the dropper under the tongue, hold for 45-60 seconds, then swallow.

For studies involving treatment or diagnosis, provide information about standard of care at Partners (e.g., BWH, MGH) and indicate how the study procedures differ from standard care. Provide information on available alternative treatments, procedures, or methods of diagnosis.

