Risks Associated with Neuropsychological and Clinical Assessment/Rating Scales

Although unlikely, it is possible that during the structured assessment or rating scales, subjects may become distressed when recalling periods of their lives or their current mood state. Subjects may also become frustrated during the neuropsychological testing. Subjects are informed that they can take a break and/or can choose to stop answering questions at any time. To mitigate any risks associated with the neurocognitive assessment or clinical ratings, clinical staff will be available to evaluate and advise the subject during study visits.

MR/fMRI/DTI/DKI/MRS

Currently, there are no known risks associated with fMRI, MRI, DTI/DKI, or MRS scanning in the 3T scanner, however, there are some areas of concern that must be addressed. First, participation in an MRI study requires subjects to be exposed to strong magnetic fields, the long-term effects of which are unknown. The magnetic fields also require caution given the risk of attraction of ferromagnetic metal objects by the high strength magnetic field. Second, some subjects express discomfort by the relatively confined space within the bore of the MR scanner. Finally, some subjects find the scanning experience unpleasant because of the noise of the gradients during MRI image acquisition. Each of these risks is present for a clinical MR scan, which are not increased by the research project proposed in this application.

CBD Administration

The administration of CBD is considered low-risk because of the add-on design of the study; in addition, previous studies of CBD administration have reported no signs of toxicity or serious side effects (Cunha et al. 1980; Consroe et al. 1991; Leweke et al. 2012; Zuardi et al. 2006 and 2009). The safety of CBD administration in pregnant women and fetuses is currently unknown; thus, female participants capable of child-bearing will be screened for pregnancy prior to the study and at each study visit. Participants will be immediately disqualified and excluded from further participation in the study if they have a positive pregnancy test at any point during the study.

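### Staff may end participation over an adverse event and must end it after a positive pregnancy test; neither provision lets the subject stop product and stay on study

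*Combined protocol and SAP*

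**What the plan says.** The safety paragraph of Research Design and Methods gives two routes out after an adverse event. The first is the subject's own choice: "A subject's participation in the trial will end if they report adverse effects of CBD or placebo administration and wish to leave the study". The second is a staff decision: "or if study staff determine that study termination is appropriate due to adverse events". In both, what ends is participation in the trial, not only dosing.

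Foreseeable Risks and Discomforts, under CBD Administration, has a third route, and it is mandatory: "Participants will be immediately disqualified and excluded from further participation in the study if they have a positive pregnancy test". The test is repeated at every visit.

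On what is measured and when, Research Design and Methods states: "At each weekly visit, individuals will complete clinical scales and have a check-in with study staff". The schedule is "five visits (baseline, and four weekly visits throughout the four-week treatment period" (closing bracket omitted here). Neuropsychological testing takes place only at baseline and at the final visit. The double-blind arms are planned at 45 full-spectrum, 15 single-compound and 15 placebo.

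Statistical Approaches names mixed model ANOVAs for the treatment effects. It does not say how scores taken after stopping product are to be used, which subjects form the analysis population, or how missing visits are handled.

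**The concern.** Stopping a product and leaving a study are separate decisions. The first protects the subject. The second also ends measurement. A plan that provides only for the second gives up data it could often keep, and gives it up selectively, because the people who leave are those who had an event.

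The week 4 visit is the post-treatment measurement for Aim 1 (anxiety and quality of life) and Aim 2 (cognition). Aim 2 has no intermediate assessment to fall back on. If one product is tolerated less well than another, exits will be unequal across arms. The arms then compared at week 4 are no longer the arms that were randomised, and without post-exit scores nobody can check how far the result has moved.

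Nothing in the design stands in the way of keeping people. CBD is added to usual treatment, which continues, so a subject off the tincture can still fill in scales and be tested.

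**Working it through.** **Is an off-product, on-study status described anywhere?** The places where it could appear are:
- the safety paragraph of Research Design and Methods: both routes end participation;
- CBD Administration: a positive pregnancy test ends participation;
- Data and Safety Monitoring: events are reported to the investigator and the IRB, and handling is left to IRB guidelines;
- Statistical Approaches: silent.

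The readable text neither offers such a status nor forbids it.

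**What one exit loses.** There are 4 post-baseline scale assessments (weeks 1 to 4).

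| Last visit completed | Scale assessments lost | Share |
|---|---|---|
| Baseline | 4 of 4 | 100% |
| Week 1 | 3 of 4 | 75% |
| Week 2 | 2 of 4 | 50% |
| Week 3 | 1 of 4 | 25% |

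Every row includes the week 4 scales and the final neuropsychological testing, unless an early-termination assessment is done that the plan does not state.

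**Share of an arm's week 4 data, per exit.**
- Placebo or single-compound: 1/15 = 6.7%.
- Full-spectrum: 1/45 = 2.2%.

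These shares are the same for a dropout of any cause. They measure one exit, not how many will occur. The plan gives no figure from which the number of adverse-event or pregnancy exits could be derived.

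**How the loss turns into bias.** Let p be the fraction of an arm that exits, S the week 4 mean of those who stay, and L the mean that those who leave would have had.
- Mean over all randomised = (1 − p)S + pL.
- Completers' mean minus that mean = p(S − L).
- For one exit this is 0.067 × (S − L) in an arm of 15 and 0.022 × (S − L) in the arm of 45.

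The bias in a between-arm contrast is the difference of the two arms' terms. It is zero if leavers resemble stayers, or if the terms are equal. It grows when tolerability differs by arm and leavers differ from stayers.

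**Are retained visits already paid for?** First, the plan's own totals reproduce.
- Hours: baseline 6–7, plus three weekly visits at 1 each, plus a last visit for which "the final study visit is estimated to take approximately 3-4 hours". That gives 6–7 + 3 + 3–4 = 12–14, as stated.
- Payments, double-blind with MRI and blood draws: baseline 75 + 75 + 25 = $175. After baseline: 3 × 50 + 75 + 75 + 25 + 50 = $375. Total 175 + 375 = $550, as stated.

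A subject who stops product straight after baseline and completes every visit therefore uses at most 3 + (3 to 4) = 6–7 hours and $375, all inside the plan.

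**The case against.** The strongest reply is that silence is not a rule. The first adverse-event route requires that the subject wants to leave, which is voluntary withdrawal and cannot be drafted away. The second is discretionary, so staff may pause product and keep the visits. A subject with a tolerable event who wishes to stay, and whom staff do not remove, simply stays. A reader might infer that every adverse event forces an exit; the text does not say that. This reply stands for adverse events, and it limits the number affected. It does not reach the pregnancy provision, which leaves no discretion.

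Exits may also be few. The dose is 3 × 10 mg = 30 mg a day, against the single doses of 300 to 600 mg cited in the background, and the documents give no evidence that tolerability differs by arm. That stands too.

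Three further readings are tempting but unsupported.
- **An expected dropout rate.** From "we will enroll up to 22 to ensure 16 completers" a reader might compute 6/22 = 27% and apply it to the randomised arms. That statement is an enrolment ceiling for a separate open-label phase and covers non-completion from any cause.
- **A proven lack of safety follow-up.** The readable text states no follow-up of events to resolution. The only scheduled visit after week 4 is for an open-label subset, who "will complete an optional 6th visit at least one week after completing the open-label phase of the clinical trial". But the IRB guidelines are not reproduced, consent pages were removed, and text next to the visit schedule is redacted; any of these may cover it. Data and Safety Monitoring also provides for contact after an abnormal MRI. That is incidental-finding handling, but it means later contact is not wholly absent.
- **Certain loss of all final data.** The remuneration text foresees termination during a visit, so some data from that visit could exist.

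Finally, using off-product scores is a choice of treatment-effect definition, and it dilutes an on-treatment contrast. This is true, and the fix below allows for it.

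**Conclusion.** The point holds as a cheap, specific improvement that the sponsor should make. The plan lets staff end participation over an adverse event and requires it after a positive pregnancy test, with no provision in either case for stopping product and continuing assessments. The size is known per exit only, as worked above. The total effect cannot be estimated and may be small.

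The conclusion rests on two assumptions: that the plan is followed as written, and that no unseen text supplies an early-termination assessment. The bias part also needs tolerability to differ by arm and leavers to differ from stayers, neither of which the documents establish. The case for change therefore rests on low cost and small arms, not on a demonstrated loss.

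**What to change.** 1. Reword the safety paragraph of Research Design and Methods and the pregnancy sentence under CBD Administration. An adverse event (by subject choice or staff decision) or a positive pregnancy test stops study product, not participation. Unless consent is withdrawn, the subject completes the remaining weekly scales and the week 4 scales and cognitive testing. MRI or any other procedure is omitted if judged unsafe. The grounds for stopping product do not change.
2. Add one line to Statistical Approaches: scores taken off product are analysed in the randomised arm, the date of last dose is recorded, and an on-product analysis is supportive.
3. Optional clarification: state whether open events are followed until resolved or stable, and whether there is a brief contact after the last dose. If the IRB guidelines or consent form already provide this, a cross-reference is enough.

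**Cost.** A protocol and consent amendment. Items 1 and 2 need no visits or payments beyond those already planned. Any contact under item 3 would be extra staff time. The scientific price is a slight dilution of the on-treatment contrast, which the supportive analysis addresses. Subjects who withdraw consent are still lost, so the plan still needs a missing-data rule for them.
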